#### **4.3 Concomitant Medications/Treatments**

##### **4.3.1 Permitted Medications**

All treatments that the investigator considers necessary for a subject's welfare may be administered at the discretion of the investigator in keeping with the community standards of medical care. All concomitant medication will be recorded on the case report form (CRF) including all prescription, over-the-counter (OTC), herbal supplements, and IV medications and fluids. If changes occur during the trial period, documentation of drug dosage, frequency, route, and date may also be included on the CRF.

All concomitant medications received within 28 days before the first dose of trial treatment and 30 days after the last dose of trial treatment should be recorded. Concomitant medications administered after 30 days after the last dose of trial treatment should be recorded for SAEs.

In general, corticosteroids (>10mg prednisone or equivalent) and other immunosuppressive medications are not permitted. However, subjects are permitted the use of topical, ocular, intra-articular, intranasal, and inhalational corticosteroids (with minimal systemic absorption). A brief (less than 3 weeks) course of corticosteroids for prophylaxis (eg, contrast dye allergy) or for treatment of non-autoimmune conditions (eg, delayed-type hypersensitivity reaction caused by a contact allergen) is permitted. Inhaled or topical steroids, and adrenal replacement steroid doses > 10 mg daily prednisone equivalent, are permitted in the absence of active autoimmune disease.

Concomitant palliative and supportive care for disease related symptoms (including bisphosphonates and RANK-L inhibitors) is allowed if initiated prior to first dose of study therapy.

#### **4.3.2 Prohibited Medications**

Subjects are prohibited from receiving the following therapies during the Screening and Treatment Phase of this trial:

- Anti-cancer systemic chemotherapy or biological therapy
- Immunotherapy not specified in this protocol
- Chemotherapy not specified in this protocol
- Investigational agents other than nivolumab
- Radiation therapy
- Systemic corticosteroids (>10mg prednisone or equivalent) or other immunosuppressive medications are not permitted unless they fall under the criteria listed in 4.3.1.

#### **4.4 Duration of Therapy**

In the absence of treatment delays due to adverse event(s), treatment may continue until one of the following criteria applies:

- Disease progression (please refer to 4.2.3 for guidance regarding treatment beyond progression),
- Intercurrent illness that prevents further administration of treatment,
- Unacceptable adverse event(s) as already described in session.

#### **4.5 Duration of Follow Up**

All patients will be followed for adverse events for 12 weeks after last dose of nivolumab, or until the patient starts a new treatment, whichever occurs first. Patients who discontinue treatment for unacceptable adverse event(s) will be followed until resolution or stabilization of the adverse event (i.e. the grade is not changing). If a patient stops treatment due to unacceptable adverse event(s) but has not demonstrated disease progression, then the patient will be followed with imaging studies every 8 weeks until the time of progression radiographically according to RECIST 1.1 criteria. In the event that a radiographic response is detected, then this event will be included as a response in the final analysis, and the time of progression used in calculation of the survival analysis. Patients will be followed for survival status every 3 months for 2 years after treatment discontinuation or until death, whichever occurs first.

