## 1.0 INTRODUCTION – BACKGROUND & RATIONALE

### 1.1 Disease Background

Adrenocortical carcinoma (ACC) is an exceedingly rare malignancy with no effective standard treatment options. ACC is responsible for 0.2% of all cancer deaths in the United States and has an estimated incidence of 0.7 cases per million per year [1, 2]. The disease incidence has a bimodal distribution with peaks in first and fourth decades with a female to male ratio 1.5-2.5:1 [3, 4]. While a growing number of patients are diagnosed with early stage and indolent disease incidentally after having abdominal CT scans, the majority of patients (40-60%) present with symptoms related to excessive hormonal production (i.e. hypercortisolism or hyperandrogenism)[3, 5]. Surgery is the treatment of choice for patients presenting with localized disease and is often followed by adjuvant chemotherapy with mitotane to mitigate the risk of disease recurrence in high-risk patients [6-8]. The group of approximately 30-70% of patients presenting with metastatic disease carry an extremely poor prognosis related to the aggressive biological behavior and lack of effective therapeutic options [3, 5]. The 5-year survival rate for this patient population is estimated at less than 15% [9].

Mitotane, the only FDA-approved drug for ACC, displays single-agent activity (10-30% tumor response rates) based on its adrenolytic activity but its broad clinical use is challenged by an unfavorable toxicity profile [10-12]. Chemotherapy has also limited efficacy in advanced disease with retrospective studies showing response rates of 10-20% [13-15]. The only phase 3 randomized clinical trial ever conducted in advanced ACC showed that mitotane combined with etoposide, doxorubicin and cisplatin (EDPM) provided additional clinical benefit compared to mitotane plus streptozocin [16]. In spite of higher tumor response rates with EDPM (23% vs. 9%) and prolongation of progression-free survival (PFS; 5 vs. 2 months), there was no significant benefit in median overall survival (OS; 14 vs. 12 months) and up to 58% of patients receiving EDPM had serious adverse events. In fact, as a clear statement to the unmet need for effective treatments, the National Comprehensive Cancer Network recommendations for first line treatment of metastatic ACC include consideration of systemic therapies in clinical trials.

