### **1.2.3 Clinical efficacy**

Nivolumab has demonstrated clinical activity as monotherapy and as combination therapy with ipilimumab in several tumor types, including RCC, melanoma, NSCLC, and some lymphomas. The majority of responses was durable and exceeded 6 months (Investigator Brochure version 2014). Nivolumab is being investigated both as monotherapy and in combination with chemotherapy, targeted therapies, and other immunotherapies.

In a phase 1 (1, 3, and 10 mg/kg nivolumab doses) dose-escalation study the 3 mg/kg dose was chosen for expanded cohorts. Among 236 patients, objective responses (ORs) (complete or partial responses [CR or PR]) were seen in NSCLC, melanoma, and RCC. ORs were observed at all doses. Median OS was 16.8 months across doses and 20.3 months at the 3 mg/kg dose. Heavily pretreated patients with NSCLC treated with nivolumab (1, 3, or 10mg/kg) achieved median OS across all dose cohorts of 9.9 months with response rates of 17% and median duration of response 17 months [35]. In addition, responses were similar between both squamous and non-squamous carcinoma cohorts in this study. A subsequent phase 3 study compared nivolumab to docetaxel in second-line treatment setting of advanced squamous cell carcinoma among 272

patients. Nivolumab arm demonstrated superior median OS (9 vs 6 months), 1 year survival rate (42 vs 24%), response rates (20 vs 9%), and significantly lower rates of grade 3-4 treatment related adverse events (7 vs 55%) [36]. These results supported the FDA approval of nivolumab for second-line treatment of advanced squamous cell carcinoma following treatment with platinum-based chemotherapy.

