#### 3.1 Inclusion Criteria

- 3.1.1 Patients must have a histologically confirmed stage IV or unresectable locally advanced adrenocortical carcinoma,
- 3.1.2 Patients must have disease progressing after treatment with at least one line of therapy including mitotane and/or chemotherapy.

Note: Patients who are deemed ineligible to receive first line treatment with mitotane and/or chemotherapy or who decline first line treatment may be eligible for this study after discussion with the PI.

- 3.1.3 Patients must have measurable disease according to the standard RECIST version 1.1. CT scans or MRIs used to assess the measurable disease must have been completed within 28 days prior to registration.
- 3.1.4 Patients must be of age  $\geq 18$  years at the time of study registration.
- 3.1.5 Patients must exhibit an ECOG performance status of 0-3.
- 3.1.6 Patients must have adequate organ and bone marrow functions:
  - leukocytes  $\geq 2,000/\text{mcl}$

- absolute neutrophil count  $\geq 1,500/\text{mcl}$
- hemoglobin  $\geq 9 \text{ g/dL}$
- platelets  $\geq 75,000/\text{mcl}$
- total bilirubin  $\leq 1.5 \times$  institutional upper limit of normal (ULN)  
(except patients with Gilbert Syndrome, who can have total bilirubin  $< 3.0 \text{ mg/dL}$ )
- AST(SGOT)/ALT(SGPT)  $\leq 3 \times$  ULN  
*NOTE: If liver metastases are present, AST/ALT  $\leq 5 \times$  ULN is permitted*
- Serum creatinine of  $< 3.0 \times$  ULN (upper limit of normal) or creatinine clearance  $> 30 \text{ mL/minute}$  (using Cockcroft/Gault formula below):  
Female CrCl =  $\frac{(140 - \text{age in years}) \times \text{weight in kg} \times 0.85}{72 \times \text{serum creatinine in mg/dL}}$   
Male CrCl =  $\frac{(140 - \text{age in years}) \times \text{weight in kg} \times 1.00}{72 \times \text{serum creatinine in mg/dL}}$

3.1.7 Patients with history of central nervous system (CNS) metastases are eligible if CNS disease has been radiographically and neurologically stable for at least 6 weeks prior to study registrations and do not require corticosteroids (of any dose) for symptomatic management

3.1.8 Females of childbearing potential (FOCBP) must have a negative serum or urine pregnancy test (minimum sensitivity 25 IU/L or equivalent units of HCG) within 24 hours prior to the start of study drug.

NOTE: A FOCBP is *any woman* (regardless of sexual orientation, having undergone a tubal ligation, or remaining celibate by choice) who meets the following criteria:

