#### **6.2.3.3 Evaluation of best overall response**

The best overall response is the best response recorded from the start of the treatment until disease progression/recurrence (taking as reference for progressive disease the smallest measurements recorded since the treatment started). The patient's best response assignment will depend on the achievement of both measurement and confirmation criteria. Responses will be assessed using CT scans or magnetic resonance imaging according to standard RECIST 1.1 criteria in order to assess disease progression. These criteria will also allow for patients who experience an initial disease flare, and as some patients who will have a delayed response may experience an initial disease flare, we will allow patients to continue receiving nivolumab beyond progression (see section 4.2.5)

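### Section 4.5 counts responses found after nivolumab is stopped for toxicity, and nothing ends the counting when the patient starts another anti-cancer drug

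*Combined protocol and SAP*

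**What the plan says.** Section 4.5 covers patients who stop for unacceptable adverse events without having progressed. They are imaged every 8 weeks until radiographic progression by RECIST 1.1, and: "In the event that a radiographic response is detected, then this event will be included as a response in the final analysis".

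The same paragraph foresees that such patients may move to another drug, but uses that event only to end adverse-event follow-up, which runs "for 12 weeks after last dose of nivolumab, or until the patient starts a new treatment, whichever occurs first". Footnote 10 to the section 5.0 table uses it only to time the End of Treatment visit.

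The other places where a limit might stand:

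- **4.3.2:** "Subjects are prohibited from receiving the following therapies during the Screening and Treatment Phase of this trial". The ban does not reach the period after nivolumab is stopped.
- **4.1:** other agents intended to treat the malignancy are barred, as part of treatment administration.
- **6.2.3.3:** "The best overall response is the best response recorded from the start of the treatment until disease progression/recurrence". The window closes at progression. Confirmation is also required, and 6.1 asks for a confirmatory scan 8 weeks after a first response.
- **6.2.1 and 10.2:** evaluability needs measurable disease, at least one dose and a re-evaluation. Later therapy is not mentioned.

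On recording, 4.3.1 covers "All concomitant medications received within 28 days before the first dose of trial treatment and 30 days after the last dose of trial treatment"; later medications are recorded only for serious adverse events.

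**The concern.** The primary endpoint is a single-arm response rate tested against 5%. Tumor shrinkage caused by a later drug says nothing about nivolumab, yet followed literally the plan includes it. Under 10.1, 3 responses in 29 is a negative trial and 4 is a positive one; at stage 1, none in 10 stops the trial and one lets it continue. A single misattributed response can therefore change the outcome at either stage.

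The drugs most likely to follow have response rates above the 5% null. Section 1.1 says: "Mitotane, the only FDA-approved drug for ACC, displays single-agent activity (10-30% tumor response rates) based on its adrenolytic activity". It gives 10-20% for chemotherapy. Inclusion criterion 3.1.2 asks for progression after mitotane and/or chemotherapy, so a patient who has had only one of them could still start the other.

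An analyst who wished to exclude such a case would be departing from a written rule with the outcome known, in a trial where the investigator assesses response (6.1). The start of the later drug might also not be in the data.

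**Working it through.** **1. The plan's own figures.** From 10.1: stop if 0 of 10 respond; declare activity if at least 4 of 29 respond; null rate 5%, alternative 20%. With true rate p, the probability of a positive trial is

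α(p) = Σ (x = 1 to 10) P[Bin(10, p) = x] × P[Bin(19, p) ≥ 4 − x].

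- Type I error, α(0.05) = 0.0468 (stated: 5%).
- Power, α(0.20) = 0.801 (stated: 80%).
- Early stop at 5%: 0.95^10 = 0.599 (stated: 60%).

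The stated design reproduces.

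**2. How close the decision is to one patient.**

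- 3/29 = 10.3%, exact 95% CI 2.2-27.4%: negative.
- 4/29 = 13.8%, exact 95% CI 3.9-31.7%: positive.
- Chance of passing stage 1 and ending at exactly 3 of 29: 8.8% if the true rate is 5%, 17.3% if it is 10%. This is the chance of standing one response short. It is not the chance of a reversal, which also needs a false response.
- If one patient is certain to be a misattributed responder, the type I error is 0.128 when that patient is in stage 2 and 0.163 when in stage 1.

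**3. Inputs for the expected effect.**

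- s, share stopping for toxicity: not given. Assumed 7-11%, borrowing the grade 3-4 treatment-related event rates quoted in 1.2.3 for squamous lung cancer (7%) and renal cell carcinoma (11%).
- w, share of those who start a new drug before progression: not given. Assumed 10-25%, with 100% as a ceiling.
- r, response rate to the new drug: 10-30%, the mitotane range in 1.1.

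Expected false responses = 29 × s × w × r. This slightly overstates, because it does not remove patients who had already responded to nivolumab.

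Apparent response rate under the null: p = 0.05 + 0.95 × s × w × r. Putting this p into α(p) gives the type I error.

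**4. Results.**

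| s | w | r | False responses | p | Type I error |
|---|---|---|---|---|---|
| 7% | 10% | 10% | 29 × 0.0007 = 0.02 | 0.0507 | 0.049 |
| 11% | 10% | 30% | 29 × 0.0033 = 0.10 | 0.0531 | 0.056 |
| 7% | 25% | 10% | 29 × 0.00175 = 0.05 | 0.0517 | 0.052 |
| 11% | 25% | 30% | 29 × 0.00825 = 0.24 | 0.0578 | 0.072 |
| 7% | 100% | 10% | 29 × 0.007 = 0.20 | 0.0567 | 0.068 |
| 11% | 100% | 30% | 29 × 0.033 = 0.96 | 0.0814 | 0.180 |

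With a cut-off at new therapy, the added term is zero and the type I error stays at 0.047.

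**The case against.** **A miscounted case needs a long chain of events.** The patient must stop for toxicity without progression, not already be a responder, start a new drug before progression, respond only afterwards, and have that response confirmed. This stands, and it is why the expected effect is small. A reader might infer from 4.5 that any later shrinkage counts. The text does not go that far: the response must come before RECIST progression, and 6.1 and 6.2.3.3 ask for confirmation. But a response to a second drug can be confirmed too.

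**The toxicity rates overstate stopping.** They come from other tumors, and 4.2.1 does not require discontinuation for most grade 3 laboratory abnormalities or for many grade 3 events lasting 7 days or less. This stands; the 100% switching rows are a ceiling.

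**The note to 3.1.2 is weaker evidence than it looks.** A reader might infer that it brings in many patients for whom mitotane and chemotherapy remain open. It admits those judged ineligible for first-line treatment, and those "who decline first line treatment may be eligible for this study after discussion with the PI". These patients cannot have, or have refused, those drugs, and they enter by exception. The stronger route is a patient treated with only one of the two, and the 10-30% range may be generous for that mix.

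**The new-treatment date is partly captured.** Within about 12 weeks of the last dose, a new treatment ends adverse-event follow-up and brings forward the End of Treatment visit, which includes a tumor assessment. Later starts have no specified record in this document. The separate data submission guidelines mentioned in 11.4 might cover them and cannot be checked here.

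**Off-drug responses are counted for good reason.** Sections 1.2.1 and 4.2.3 expect delayed responses to immunotherapy. That supports counting after nivolumab stops. It does not support counting after another active drug starts.

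**Mitotane during treatment.** A reader might infer that the plan also leaves open mitotane taken alongside nivolumab. Section 4.1 already bars other agents given to treat the malignancy, and the documents do not discuss mitotane for hormonal symptoms. No change is asked for there.

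**Conclusion.** The point holds as a fault in a stated counting rule for the primary endpoint: a confirmed response to a drug started after nivolumab, and before progression, would be counted as a nivolumab response.

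The likely size is small: a fraction of one false response, and a type I error modestly above its design value under the 10-25% switching assumption. Even the lower end of the ceiling, with every stopper switching, adds only about two percentage points. All of these figures rest on assumed stopping and switching rates, and on switching being unrelated to whether the patient would have responded to nivolumab.

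A reader might infer a large inflation of the type I error. The documents do not support that. A value near 0.33, for example, would need 20% of all patients to stop, switch before progression and then respond at 30%; that 20% is nearly double the higher toxicity rate quoted. The case for acting is that a single such patient could decide the trial and the rule costs little to correct in advance.

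**What to change.** Add to 4.5: *A response first documented after the start of any new anti-cancer treatment, including mitotane, is not counted as a response; it is listed separately.*

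Record the name and start date of the first new anti-cancer treatment for as long as imaging follow-up continues, beyond the 30-day limit in 4.3.1.

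This costs one sentence and one data field. Sample size, decision rule, accrual and patient care do not change, and responses seen off nivolumab before any new drug still count. The drawback is that a genuine delayed nivolumab response first seen after a switch is no longer counted. With four responses decisive, that loss could also matter, which is why such cases should be listed so that readers can judge them.

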#### **4.6 Removal of Subjects from Study Treatment and/or Study as a Whole**

Patients can be taken off the study treatment and/or study as a whole at any time at their own request, or they may be withdrawn at the discretion of the investigator for safety, behavioral or administrative reasons. The reason(s) for discontinuation must be clearly documented on the appropriate eCRF and may include:

- Patient voluntarily withdraws from treatment (follow-up permitted)
- Patient withdraws consent (no follow-up permitted)
- Patient is unable to comply with protocol requirements
- Patient demonstrates disease progression (per parameters above)
- Patient experiences unacceptable toxicity
- Treating physician determines that continuation on the study would not be in the patient's best interest
- Patient becomes pregnant

- Patient develops a second malignancy that requires treatment which would interfere with this study
- Patient becomes lost to follow-up (LTF)

**4.7 Patient Replacement**

Any patient who signs consent but does not receive study treatment may be replaced.

## 5.0 STUDY PROCEDURES

	Screening 	On Treatment  (1 cycle = 28 days)						Off Treatment	
Time Period	Baseline	Cycle 1		Cycle 2		Cycle 3+		End of Treatment 	Follow-up 
		D1 (±3 days)	D15 (±3 days)	D1 (±3 days)	D15 (±3 days)	D1 (±3 days)	D15 (±3 days)		
Assessment or Activity									
Informed Consent	X								
Medical history	X							X	
Physical exam 	X	X	X	X		X		X	
ECOG status	X	X	X	X		X		X	
Adverse Events & ConMeds	X	X	X	X	X	X	X	X	
Toxicity assessment	X	X	X	X	X	X	X	X	
Tumor Assessments 	X					X 		X	
CBC with diff 	X	X	X	X	X	X	X	X	
Chemistry panel 	X	X	X	X	X	X	X	X	
TSH 	X								
Pregnancy test 	X	X 							
Nivolumab administration 		X	X	X	X	X	X		
Correlative blood samples		X 			X 				
Archival tissue collection 	X								
Survival status									X

 CBC with diff and Chemistry panel should be within 14 days of registration; all other screening procedures should take place within 28 days of registration. CBC should include WBC, Hemoglobin, Platelets, ANC, ALC. Chemistry panel should include glucose, calcium, albumin, ALT, AST, sodium, potassium, total bilirubin, alk phose, and creatinine.

 Includes vital signs (pulse, respirations, blood pressure) and height (baseline only) and weight.

 CT or MRI (per treating investigator's discretion) will take place within 28 days of registration; the same modality used at baseline should be used throughout. Tumor assessment will be performed at Cycle 3 Day 1 (- 7 days) and every 2 cycles (- 7 days) thereafter, regardless of dosing schedule for the first 13 months then every 3 cycles (-7 days) until progression or treatment discontinuation whichever occurs later. Tumor assessments will incorporate both RECIST and clinical criteria. Brain MRI is the preferred imaging method for evaluating CNS metastasis, and assessment is required during screening in all eligible subjects with history of CNS involvement. If PD is confirmed at any time, see section 4.2.3 on how to determine whether patient can be considered for further treatment. If patient continues, scans should be obtained every 8 weeks until PD is confirmed by 2 consecutive scans.

-  If TSH is abnormal, free T4 should be tested
-  Serum or urine test for females of child-bearing potential must be completed at screening and within 24 hours of treatment.
-  Nivolumab will be administered IV at 240mg over 30 minutes every two weeks.
-  A correlative blood sample will be drawn pre-dose at C1D1 and C2D15. Please see separate lab manual for details.
-  Archival tissue will be collected at baseline if available. Please see separate lab manual for details.
-  Treatment will continue until confirmed disease progression, unacceptable toxicity, or withdrawal of consent. Study assessments may take place within 24 hours of scheduled treatment if needed.
-  End of Treatment visit will occur approximately 12 weeks after stopping nivolumab treatment, or until the patient starts new treatment, whichever occurs first.
-  Patients will be followed (either by routine clinic visit or by phone) every 2 weeks while on treatment and every 3 months for up to 2 years while off treatment to document survival and disease progression. Adverse events will be followed for the first 12 weeks after stopping treatment.

